## **8.2. Statistical Analyses**

The day of surgery will be labeled Day 1. The days before surgery will be labeled Day -1, Day -2, etc.

Besides the analyses described in this document, other exploratory analyses may be performed.

### **8.2.1. Analyses for Efficacy**

All primary and secondary endpoints will be subjected to subgroup analysis, where SA4Ag and placebo will be compared at each level of the subgroup. Fifteen subgroups will be examined:

1. Race.
2. Age group.
3. Sex.
4. Ethnicity.
5. Smoking status.
6. Country.
7. CCI score.
8. Colonization at the time of surgery (performed for any *S aureus*).
9. Colonization at the time of surgery (performed for MRSA).
10. Colonization at the time of surgery (performed for MSSA).
11. Timing of the surgery after vaccination.

12. Presurgery decolonization (any/none).
13. Intrawound application of antibiotic (yes/no).
14. High-enrolling investigator sites (yes/no); the number of mITT subjects will be compiled by site. Sites with  $\geq 50$  mITT subjects will be considered high-enrolling sites.
15. High-attack rate investigator sites (yes/no); the number of mITT subjects with any PDI (BSI, deep incisional or organ/space SSI, superficial SSI, or ISA disease) will be compiled by site. The median of the nonzero values will be computed (only nonzero values will be included because multiple sites are expected to not have any PDI). Sites with the median or higher will be considered high-attack rate sites.

The subgroup analysis by timing of surgery after vaccination in the interval 1-14 days should be understood as an interval of 9-14 days in the PP efficacy population, because subjects with timing of 1-8 days after vaccination will be excluded from the PP efficacy population.

Subgroup analyses by site are not proposed because of the expected sparseness of cases.

Subgroup analyses will be performed in both the PP and mITT efficacy populations.

All analyses for 1 endpoint in 1 population, ie, all subjects plus every level of each subgroup, will be included in the same table.

Subgroup analyses will not be performed for postoperative ISA disease based on baseline *S aureus* colonization, because these are exploratory endpoints. Instead, baseline *S aureus* colonization will be included as a subgroup in the analyses of postoperative ISA disease.

Efficacy analyses are summarized in Table 14.

**Table 14. Summary of Efficacy Analyses in the Per-Protocol Population**

Endpoint	Population	Statistical Method	Model/ Covariates/ Strata	Missing Data	Interpretation/ Comments
Postoperative Staphylococcus aureus BSI and/or deep incisional or organ/space SSI occurring within 90 days	PP	Binomial	N/A	N/A	Primary efficacy endpoint
Postoperative S aureus BSI and/or deep incisional or organ/space SSI occurring within 180 days	PP	Binomial	N/A	N/A	Secondary endpoint
Postoperative S aureus SSI occurring within 90 days	PP	Binomial	N/A	N/A	Secondary endpoint
Postoperative S aureus SSI occurring within 180 days	PP	Binomial	N/A	N/A	Secondary endpoint
Postoperative ISA disease occurring within 90 days	PP	Binomial	N/A	N/A	Exploratory

**Table 14. Summary of Efficacy Analyses in the Per-Protocol Population**

Endpoint	Population	Statistical Method	Model/ Covariates/ Strata	Missing Data	Interpretation/ Comments
Postoperative ISA disease occurring within 180 days	PP	Binomial	N/A	N/A	Exploratory
Postoperative Staphylococcus aureus BSI and/or deep incisional or organ/space SSI occurring within 90 days based on baseline S aureus colonization	PP	Binomial	N/A	N/A	Exploratory
Postoperative Staphylococcus aureus BSI and/or deep incisional or organ/space SSI occurring within 180 days based on baseline S aureus colonization	PP	Binomial	N/A	N/A	Exploratory
Postoperative BSI and/or deep incisional or organ/space SSI or superficial SSI, attributable to any pathogen, occurring within 90 days	PP	Binomial	N/A	N/A	Exploratory
Postoperative BSI and/or deep incisional or organ/space SSI or superficial SSI, attributable to any pathogen, occurring within 180 days	PP	Binomial	N/A	N/A	Exploratory

Abbreviations: BSI = bloodstream infection; ISA = invasive *Staphylococcus aureus*; N/A = not applicable; PP = per-protocol; SSI = surgical-site infection.

The analyses will be repeated in the mITT efficacy populations (Table 15).

**Table 15. Summary of Efficacy Analyses in the mITT Efficacy Populations**

Endpoint	Population	Statistical Method	Model/ Covariates/ Strata	Missing Data	Interpretation/ Comments
Postoperative Staphylococcus aureus BSI and/or deep incisional or organ/space SSI occurring within 90 days	mITT Restricted mITT	Binomial	N/A	N/A	Secondary efficacy endpoint
Postoperative S aureus BSI and/or deep incisional or organ/space SSI occurring within 180 days	mITT Restricted mITT	Binomial	N/A	N/A	Secondary endpoint

**Table 15. Summary of Efficacy Analyses in the mITT Efficacy Populations**

Endpoint	Population	Statistical Method	Model/ Covariates/ Strata	Missing Data	Interpretation/ Comments
Postoperative S aureus SSI occurring within 90 days	mITT, Restricted mITT	Binomial	N/A	N/A	Secondary endpoint
Postoperative S aureus SSI occurring within 180 days	mITT, Restricted mITT	Binomial	N/A	N/A	Secondary endpoint
Postoperative ISA disease occurring within 90 days	mITT, Restricted mITT	Binomial	N/A	N/A	Exploratory
Postoperative ISA disease occurring within 180 days	mITT, Restricted mITT	Binomial	N/A	N/A	Exploratory
Postoperative ISA disease occurring within 90 days based on baseline S aureus colonization	mITT, Restricted mITT	Binomial	N/A	N/A	Exploratory
Postoperative ISA disease occurring within 180 days based on baseline S aureus colonization	mITT, Restricted mITT	Binomial	N/A	N/A	Exploratory
Postoperative BSI and/or deep incisional or organ/space SSI or superficial SSI, attributable to any pathogen, occurring within 90 days	mITT, Restricted mITT	Binomial	N/A	N/A	Exploratory
Postoperative BSI and/or deep incisional or organ/space SSI or superficial SSI, attributable to any pathogen, occurring within 180 days	mITT, Restricted mITT	Binomial	N/A	N/A	Exploratory
Overrun	mITT, Restricted mITT	Binomial	N/A	N/A	Exploratory; includes cases arriving after the planned 48

Abbreviations: BSI = bloodstream infection; ISA = invasive *Staphylococcus aureus*; N/A = not applicable; SSI = surgical-site infection.

NNT analyses will be reported for each endpoint in both the PP and mITT populations (see [Table 16](#)). NNTs will not be compiled for subgroups. All NNT analyses for the same population will be presented in the same table.

**Table 16. Summary of Number-Needed-to-Treat Analyses for Efficacy Endpoints**

Endpoint	Population	Statistical Method	Model/ Covariates/ Strata	Missing Data	Interpretation/ Comments
NNT for each efficacy endpoint	PP	Reciprocal of difference in proportions and associated 95% CI	N/A	N/A	One table for all NNT endpoint analyses
NNT for each efficacy endpoint	mITT	Reciprocal of difference in proportions and associated 95% CI	N/A	N/A	One table for all NNT endpoint analyses
NNT for each efficacy endpoint	Restricted mITT	Reciprocal of difference in proportions and associated 95% CI	N/A	N/A	One table for all NNT endpoint analyses

Abbreviations: N/A = not applicable; NNT = number needed to treat; PP = per-protocol.

Only the primary and secondary endpoints will be subjected to sensitivity analyses. Missing data sensitivity analyses will not be performed on subgroups. Sensitivity analyses will be performed for both the PP and mITT populations. There will be 12 sets of sensitivity analyses.

All sensitivity analyses for a given endpoint in a given population should appear on the same table. The corresponding efficacy analysis described in [Table 14](#) (PP efficacy population) or [Table 15](#) (mITT efficacy population) should be included for ease of review. Sensitivity analyses are summarized in Table 17.

**Table 17. Summary of Sensitivity Analyses**

Endpoint	Population	Statistical Method	Model/ Covariates/ Strata	Missing Data	Interpretation/ Comments
Postoperative Staphylococcus aureus BSI and/or deep incisional or organ/space SSI occurring within 90 days	PP, mITT, Restricted mITT	Best case, worst case, observed, MAR, MNAR, follow-up time	N/A	N/A	Endpoint in PP population is primary endpoint
Postoperative S aureus BSI and/or deep incisional or organ/space SSI occurring within 180 days	PP, mITT, Restricted mITT	Best case, worst case, observed, MAR, MNAR, follow-up time	N/A	N/A	Secondary endpoint
Postoperative S aureus SSI occurring within 90 days	PP, mITT, Restricted mITT	Best case, worst case, observed, MAR, MNAR, follow-up time	N/A	N/A	Secondary endpoint
Postoperative S aureus SSI occurring within 180 days	PP, mITT, Restricted mITT	Best case, worst case, observed, MAR, MNAR, follow-up time	N/A	N/A	Secondary endpoint

Abbreviations: BSI = bloodstream infection; MAR = missing at random; MNAR = missing not at random; N/A = not applicable; PP = per-protocol; SSI = surgical-site infection.

**8.2.2. Analysis of Safety Data**

The tier method for AEs is described in [Section 8.1.2.1](#).

All analyses will be performed on the safety population.

**8.2.2.1. Adverse Events and Serious Adverse Events**

Tier 1 AEs will be identified in the safety review plan.

Tier 1-3 methodology will be applied to analyses from 3 intervals: vaccination until surgery, vaccination until Day 42, and surgery until Day 42. Tier 3 methodology will be applied to newly diagnosed chronic medical disorders from Day 42 until Day 180.

Tier 1, Tier 2, and Tier 3 analyses will be repeated for each level of sex, race, age group, and ethnicity. All levels of the subgroup will be included in the same table, eg, males and females in the same table, in order to facilitate review.

Subgroup analyses are not proposed for newly diagnosed chronic medical disorders, SAEs, or deaths.

Subgroup analyses are not proposed for AE rates before surgery, because this is a sensitivity analysis.

All analyses will be performed in the safety population.

AE analyses are summarized in Table 18.

**Table 18. Summary of Adverse Event Analyses**

Endpoint	Population	Statistical Method	Model/ Covariates/ Strata	Missing Data	Interpretation/ Comments
Proportions of subjects with AEs from vaccination until day of surgery	Safety	Tier 1-3	Vaccine group	N/A	Assess safety of SA4Ag until surgery
Proportions of subjects with AEs from vaccination until Day 42	Safety	Tier 1-3	Vaccine group	N/A	Assess safety of SA4Ag from vaccination until Day 42 after surgery
Proportions of subjects with AEs from day of surgery until Day 42	Safety	Tier 1-3	Vaccine group	N/A	Assess safety of SA4Ag for 42 days after surgery
Proportions of subjects with newly diagnosed chronic medical disorders from Day 42 until Day 180	Safety	Tier 2-3	Vaccine group	N/A	Assess safety of SA4Ag
Rates of AEs per 100 or 1000 days from vaccination until day of surgery	Safety	Poisson regression	Vaccine group	N/A	Surgery follows vaccination in 10-60 days, so this analysis will account for differing exposures among subjects

**Table 18. Summary of Adverse Event Analyses**

Endpoint	Population	Statistical Method	Model/ Covariates/ Strata	Missing Data	Interpretation/ Comments
SAEs and deaths from vaccination until day of surgery	Safety	Tier 2-3	Vaccine group	N/A	Assess safety of SA4Ag
SAEs and deaths from vaccination until Day 180	Safety	Tier 2-3	Vaccine group	N/A	Assess safety of SA4Ag
SAEs and deaths from surgery until Day 180	Safety	Tier 2-3	Vaccine group	N/A	Assess safety of SA4Ag
Deaths associated with Staphylococcus aureus	Safety	Fisher exact	Vaccine group	N/A	Denominator will be number of deaths
Proportions of subjects with AEs from vaccination until day of surgery, by subgroup	Safety	Tier 1-3	Vaccine group	N/A	Assess safety of SA4Ag from vaccination until surgery
Proportions of subjects with AEs from vaccination until Day 42, by subgroup	Safety	Tier 1-3	Vaccine group	N/A	Assess safety of SA4Ag from vaccination until Day 42 after surgery
Proportions of subjects with AEs from day of surgery until Day 42, by subgroup	Safety	Tier 1-3	Vaccine group	N/A	Assess safety of SA4Ag for 42 days after surgery

Abbreviation: N/A = not applicable.

Tier 1 and Tier 2 AEs will have risk differences plotted. All risk differences will be calculated as SA4Ag minus placebo.

- Tier 1 figures will have the footnotes “95% confidence intervals are provided to help gauge the precision of the estimates for risk difference,” “p-Values and confidence intervals are not adjusted for multiplicity and should be used for screening purpose only,” and “Risk difference is computed as SA4Ag minus placebo.”
- Tier 2 figures will have the footnotes “95% Confidence intervals are provided to help gauge the precision of the estimate for the risk difference,” “They are not adjusted for multiplicity and should be used for estimation purpose only,” and “Risk difference is computed as SA4Ag minus placebo.”

The EAC will adjudicate events contributing to ISA disease. Events that are not primary or secondary endpoints associated with surgery will be included in the AE/SAE tables. However, since these AEs will be adjudicated, a separate compilation will be performed, further classifying each of these conditions as “associated with *S aureus*,” with responses being “yes,” “no,” or “not determined.” AE methodology will be Tier 3 because a small number of events is expected. Compilations will be performed over the same 3 time intervals as AEs.

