- g. Serum or capillary; fasting value required preoperatively.
- h. Physical examination includes general appearance; musculoskeletal; skin; head, eyes, ears, nose, and throat; heart; lungs; abdominal; neurological; and lymph nodes.
- i. Only applicable for women of childbearing potential. Pregnancy testing may be performed on urine or serum samples.
- j. Record the surgical indication and the planned index surgical procedure. Postoperatively, record the actual index surgical procedure.
- k. Immunogenicity blood draw and colonization swabs must be collected before vaccination at Visit 1 (window: 7 days) and before surgery at Visit 2.
- l. Refer to the respective study visit as detailed in [Section 6](#).
- m. Daily observation for PDIs, AEs, and organ failure events as detailed in [Section 6.3.1.2.1](#).
- n. The e-diary should be collected and AE data reviewed with the subject prior to surgery.
- o. Refer to Appendix 4.

SCHEDULE OF ACTIVITIES FOR ADVERSE AND STUDY EVENT REPORTING

The Schedule of Activities for Adverse and Study Event Reporting table provides an overview of the protocol safety reporting requirements. Refer to the Study Procedures ([Section 6.1](#)) and Assessments ([Section 7](#)) sections of the protocol for detailed information on each procedure and assessment required for compliance with the protocol.

Table 2. Schedule of Activities for Adverse and Study Event Reporting

Visit ID	1	2			3	4	5	6
Protocol Activity	Enrollment and Day of Vaccination	Index Hospital Admission			Day 21 Telephone Contact	Day 42 Postoperative Evaluation	Day 90 Postoperative Evaluation	Day 180 Postoperative Evaluation
		Day of Surgery	Day After Surgery	Day of Discharge				
Study Day	Day -60 to Day -10	Day 1	Day 2	(Day Variable)	Day 21	Day 42	Day 90	Day 180
Visit Window	Day -60 to Day -10	N/A	N/A	N/A	Day 18 to Day 26	Day 35 to Day 49	Day 83 to Day 97	Day 178 to Day 192
Local reactions and systemic events collected in the e-diary	From the day of vaccination for a total of 10 days ^a							
Adverse events	AEs from informed consent to the Day 42 postoperative evaluation							
						Newly diagnosed chronic medical disorders from the Day 42 postoperative evaluation to the Day 180 postoperative evaluation		
Serious adverse events	SAEs from informed consent to the Day 180 postoperative evaluation							
Protocol-defined infection events	PDI events from after surgery to the Day 180 postoperative evaluation							

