7.1. Efficacy Assessments

7.1.1. PDI Events

All subjects who undergo the index surgical procedure will be monitored for PDIs after surgery until the Day 180 postoperative evaluation.

[figure not shown]
The investigator will review all suspected PDIs against the clinical criteria provided in Appendix 1. Where the clinical criteria are met, the following procedures will be conducted:

- Notify the sponsor that a PDI event has occurred.
- Complete the requirements for a BSI/SSI event ([Section 6.4.2](#)) or an ISA event ([Section 7.1.1.2](#)).
- Report the PDI event in the CRF.

If an infection occurs after discharge from the index hospital, and the infection is managed or treated by a noninvestigator physician or at a nonstudy hospital, the study investigator will contact the treating noninvestigator physician/hospital to obtain the information required (eg, medical or hospital records, clinical, diagnostic, and microbiological data) to determine whether the infection meets PDI clinical criteria. If the clinical criteria are met, the investigator will complete the PDI event report noted above and notify the sponsor.

For the purposes of this study, PDIs will include all the infections listed in Table 6 and Table 7. As shown in Figure 1, the relationships between ISA, BSI, and SSI overlap, insofar as all BSI and SSI, with the exception of superficial SSI, are considered to be ISA disease.

Figure 1. Protocol-Defined Infections (Venn Diagram)

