## 6.2. Safety Endpoints

### 6.2.1. Adverse Events and Serious Adverse Events

AE analyses will be performed for the following intervals:

- From the day of vaccination until the day of surgery
- From the day of vaccination until the Day 42 postoperative evaluation
- From the day of surgery until the Day 42 postoperative evaluation
- From the Day 42 postoperative evaluation until the Day 180 postoperative evaluation (newly diagnosed chronic medical disorders only)

Analyses for serious adverse events (SAEs) and deaths will be performed for the following intervals:

- From vaccination until the day of surgery
- From vaccination until the Day 180 postoperative evaluation
- From the day of surgery until the Day 180 postoperative evaluation

Deaths will be categorized as associated with *S aureus* infection or not associated with *S aureus* infection.

Statistical methodology for AEs is described in [Section 8.1.2.1](#).

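### The S aureus-association table of adjudicated non-endpoint infections stops at Day 42, although these infections are followed to Day 180

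*SAP*

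**What the plan says.** SAP 8.2.2.1, in the text after Table 18, notes that the EAC adjudicates events contributing to ISA disease. Those that are not primary or secondary endpoints go into the AE and SAE tables. In addition, "since these AEs will be adjudicated, a separate compilation will be performed, further classifying each of these conditions" by association with S aureus (yes, no or not determined), using Tier 3 methods because few events are expected. On timing the SAP says: "Compilations will be performed over the same 3 time intervals as AEs".

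Earlier in the same section those intervals are named: "Tier 1-3 methodology will be applied to analyses from 3 intervals: vaccination until surgery, vaccination until Day 42, and surgery until Day 42". SAP 6.2.1 lists a fourth AE interval, Day 42 to Day 180, but restricts it to newly diagnosed chronic medical disorders. SAEs and deaths have their own set of three intervals in SAP 6.2.1, two of which run to Day 180.

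The follow-up of the infections themselves is longer. Under protocol 7.1.1, operated subjects "will be monitored for PDIs after surgery until the Day 180 postoperative evaluation". Protocol Table 2 gives the same period: "PDI events from after surgery to the Day 180 postoperative evaluation". Protocol 2.5 and 7.1.1.2 send all PDIs to the EAC, and 7.1.1.2 asks that the PDIs in Table 7 be reported as AEs or SAEs whatever the pathogen.

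**The concern.** The Day 42 limit belongs to general AE recording, which protocol 8.2 ends at Visit 4. It does not apply to PDIs, which are sought at the Day 90 and Day 180 visits, entered in the CRF and adjudicated. The SAP sentence carries the AE window over to events that are collected for more than four times as long.

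If the sentence is followed as written, a remote osteomyelitis, pneumonia or endocarditis with onset on, say, Day 100 is adjudicated for its relation to S aureus, but that result does not reach the table planned to display it. At stake is a complete, arm-by-arm account of adjudicated non-endpoint infections in the safety population over the period in which they were collected. No primary or secondary efficacy result depends on it.

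**Working it through.** **1. Which three intervals are meant.** The plan's own count is 3. The interval sentence in SAP 8.2.2.1 lists three, and Table 18 has three AE-proportion rows apart from the subgroup rows and the chronic-disorder row. These agree, and the latest end point is Day 42.

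The count alone does not settle the matter, because SAEs and deaths also have three intervals:

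| Set | Intervals | Latest end |
|---|---|---|
| AEs (SAP 8.2.2.1, Table 18) | vaccination-surgery; vaccination-Day 42; surgery-Day 42 | Day 42 |
| SAEs and deaths (SAP 6.2.1) | vaccination-surgery; vaccination-Day 180; surgery-Day 180 | Day 180 |

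The sentence refers to AEs, and the same section attaches the number three to the AE set: "3 intervals: vaccination until surgery, vaccination until Day 42, and surgery until Day 42". The AE set is the textual reading.

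**2. Follow-up not covered.** Inputs: last covered day 42; surveillance to Day 180 (protocol 7.1.1, Table 2); Day 1 is the day of surgery (SAP 6.1).

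- Days covered: 42/180 = 23.3%
- Days not covered: 180 - 42 = 138; 138/180 = 76.7%
- Day 42 visit held on Day 35 or Day 49 (the ends of its window): 145/180 = 80.6%, or 131/180 = 72.8%
- Day 180 visit held on Day 178 or Day 192: (178 - 42)/178 = 76.4%, or (192 - 42)/192 = 78.1%
- With a surgery-to-Day 180 interval added: 0 days not covered

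These are shares of calendar time. The documents give no onset-time distribution, so the share of infections cannot be calculated.

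**3. Where an infection with onset on Day 100 would appear.**

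| Event | Planned outputs that show it | S aureus association shown in safety population? |
|---|---|---|
| Organ/space SSI from the index incision, non-S aureus pathogen | any-pathogen BSI/SSI endpoint within 180 days (PP, mITT, restricted mITT) | not applicable; belongs to the SSI analyses |
| Remote infection, confirmed S aureus | ISA disease within 180 days (exploratory; PP, mITT, restricted mITT); SAE tables if serious | no |
| Pneumonia, non-S aureus or undetermined, serious | SAE tables to Day 180 | no |
| Pneumonia, non-S aureus or undetermined, nonserious | none | no |

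The last two rows are the core of the gap. The ISA endpoint counts only microbiologically confirmed S aureus (SAP 2.2), and the any-pathogen endpoint covers only BSI and SSI (SAP 6.1.3). The Day 180 SAE tables have no planned split by S aureus association, and the AE tables stop at Day 42. A nonserious late event could still be listed if it qualified as a newly diagnosed chronic disorder, but again without the classification.

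**The case against.** The strongest objection is that little is actually hidden, and most of it stands.

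- Deep infections of tissue opened at the index surgery are organ/space SSIs under protocol 7.1.1.1, and SSIs of any pathogen are analysed to 180 days.
- Confirmed S aureus ISA disease is analysed to 180 days in mITT, which is vaccinated subjects who underwent spinal surgery.
- Serious late events enter the SAE tables to Day 180 by vaccine group.
- Deaths are categorised by S aureus association with analyses to Day 180, and multiple-organ failure has its own infection and pathogen split with no stated Day 42 cut.
- The table is minor by design: Tier 3, incidence only.

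A reader might therefore infer too much from the gap, for example that a late excess of serious infection on vaccine would go unseen, or that 77% of these infections are dropped. The documents support neither. Serious events are tabulated to Day 180, and 77% is a share of days.

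A second objection is that the SAP may have meant the SAE intervals, since the paragraph mentions both AE and SAE tables. This does not stand on the text, which says AEs. If the SAE set was intended, the sentence still needs correcting.

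**Conclusion.** The point holds as a gap in one safety table. As written, the S aureus-association compilation omits Days 43-180: 138 of 180 days, 77%, or 73% to 81% across the Day 42 visit window. Two things are lost. One is the S aureus-association classification, in the safety population, of late non-endpoint infections. The other is any tabulation of late nonserious events outside BSI and SSI that are non-S aureus or undetermined. The number of such events is unknown, and the SAP itself expects few over the table as a whole. The conclusion assumes that the three intervals are the AE set named in the same section. It does not touch the primary or secondary efficacy analyses, and it does not mean that late infections disappear from safety reporting.

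**What to change.** Amend the closing sentence of SAP 8.2.2.1 so that the compilation is performed over the three planned AE intervals and also from surgery to the Day 180 evaluation, an interval SAP 6.2.1 already defines for SAEs and deaths. Keep the planned intervals, so that the table stays comparable with the AE tables, and keep the safety-population denominator. A new cut at Day 43 or a denominator of operated subjects is not needed to close the gap.

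The cost is one SAP sentence and one further block in a table shell. The events are already collected and adjudicated to Day 180, so no new data or procedures are required.
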